9 DOSING DELAYS/DOSE MODIFICATIONS

Dose Modifications for Nivolumab

Dose modifications are not allowed for nivolumab.

Dose Delay Criteria for Nivolumab

Tumor assessments should continue per protocol schedule, even if dosing is delayed. Treatment delays will be recorded, but the total duration of therapy will be up to two years, regardless of the number of cycles. Nivolumab administration should be delayed for the following:

- Any Grade ≥ 2 non-skin, drug-related AE, with the following exception:
 - Grade 2 drug-related fatigue or laboratory abnormalities do not require a treatment delay
- Grade 2 drug-related creatinine, AST, ALT, or TBILI abnormalities
- Any Grade 3 skin, drug-related AE
- Any Grade 3 drug-related laboratory abnormality (excluding AST, ALT, or TBILI), with the following exceptions for lymphopenia or asymptomatic amylase or lipase:
 - Grade 3 lymphopenia does not require dose delay
 - Any Grade ≥ 3 drug-related amylase or lipase abnormality that is not associated with symptoms or clinical manifestations of pancreatitis does not require dose delay
- Any AE, laboratory abnormality, or intercurrent illness which, in the judgment of the investigator, warrants delaying the dose of study medication [L]
[SEP]

Participants who require delay of nivolumab should be re-evaluated weekly or more frequently if clinically indicated, and resume nivolumab dosing when re-treatment criteria are met.

Criteria to Resume Dosing for Nivolumab

Participants may resume treatment with study drug when the drug-related AE(s) resolve to Grade ≤ 1 or baseline value, with the following exceptions:

- Participants may resume treatment in the presence of Grade 2 fatigue.
- Participants who have not experienced a Grade 3 drug-related skin AE may resume treatment in the presence of Grade 2 skin toxicity.
- For participants with Grade 2 AST, ALT, or TBILI elevations, dosing may resume when laboratory values return to baseline and management with corticosteroids, if needed, is complete.
- Participants with combined Grade 2 AST/ALT AND TBILI values meeting discontinuation parameters should have treatment permanently discontinued.

Columbia University Medical Center
Herbert Irving Comprehensive Cancer Center
Version Date: January 30, 2024

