- Drug-related pulmonary toxicity, diarrhea, or colitis must have resolved to baseline before treatment is resumed. Participants with persistent Grade 1 pneumonitis after completion of a steroid taper over at least 1 month may be eligible for retreatment.
- Participants with drug-related endocrinopathies adequately controlled with only physiologic hormone replacement may resume treatment after consultation with the principal investigator.

Recommended Dose Modifications for Nivolumab

Event	Severity*	Dose modification
Colitis	Grade 2 or 3 diarrhea or colitis	Withhold dose ^a
	Grade 4 diarrhea or colitis	Permanently discontinue
Pneumonitis	Grade 2 pneumonitis	Withhold dose ^a
	Grade 3 or 4 pneumonitis	Permanently discontinue
Hepatitis	Aspartate aminotransferase (AST)/or alanine aminotransferase (ALT) more than 3 and up to 5 times the upper limit of normal or total bilirubin more than 1.5 and up to 3 times the upper limit of normal	Withhold dose ^a
	AST or ALT more than 5 times the upper limit of normal or total bilirubin more than 3 times the upper limit of normal	Permanently discontinue
Hypophysitis	Grade 2 or 3 hypophysitis	Withhold dose ^a
	Grade 4 hypophysitis	Permanently discontinue
Adrenal insufficiency	Grade 2 adrenal insufficiency	Withhold dose ^a
	Grade 3 or 4 adrenal insufficiency	Permanently discontinue
Type 1 Diabetes Mellitus	Grade 3 hyperglycemia	Withhold dose ^a
	Grade 4 hyperglycemia	Permanently discontinue
Nephritis and renal dysfunction	Serum creatinine more than 1.5 and up to 6 times the upper limit of normal	Withhold dose ^a
	Serum creatinine more than 6 times the upper limit of normal	Permanently discontinue
Skin	Grade 3 rash or suspected Stevens-Johnson syndrome (SJS) or toxic epidermal necrolysis (TEN)	Withhold dose ^a
	Grade 4 rash or confirmed SJS or TEN	Permanently discontinue
Encephalitis	New-onset moderate or severe neurologic signs or symptoms	Withhold dose ^a
	Immune-mediated encephalitis	Permanently discontinue
Other	Other Grade 3 adverse reaction: 1. First occurrence 2. Recurrence of same Grade 3 adverse reactions	1. Withhold dose ^a 2. Permanently discontinue
	Life threatening or Grade 4 adverse reaction	Permanently discontinue

Columbia University Medical Center
Herbert Irving Comprehensive Cancer Center
Version Date: January 30, 2024

	Requirement for 10 mg per day or greater prednisone or equivalent for more than 12 weeks	Permanently discontinue

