	Persistent Grade 2 or 3 adverse reactions lasting 12 weeks or longer	Permanently discontinue

*Toxicity was graded per National Cancer Institute Common Terminology Criteria for Adverse Events. Version 4.0 (NCI CTCAE v4).

^a Resume treatment when adverse reaction returns to Grade 0 or 1.

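### Section 9 gives two restart rules, and the dose-table footnote is looser than the resume criteria for diarrhea/colitis, pneumonitis and liver-test holds

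*Combined protocol and SAP*

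**What the plan says.** Section 9 handles restart after a hold in two places.

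**Text.** Dose Delay Criteria calls for at least weekly re-evaluation of held participants and tells sites to "resume nivolumab dosing when re-treatment criteria are met". Criteria to Resume Dosing then gives a general rule, that drug-related events "resolve to Grade ≤ 1 or baseline value, with the following exceptions". The exceptions that matter here are:

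- Grade 2 AST, ALT or bilirubin: "dosing may resume when laboratory values return to baseline and management with corticosteroids, if needed, is complete".
- Lung and bowel: "Drug-related pulmonary toxicity, diarrhea, or colitis must have resolved to baseline before treatment is resumed".
- Pneumonitis that stays at Grade 1: "Participants with persistent Grade 1 pneumonitis after completion of a steroid taper over at least 1 month may be eligible for retreatment".

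Another exception is more permissive: "Participants with drug-related endocrinopathies adequately controlled with only physiologic hormone replacement may resume treatment after consultation with the principal investigator".

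**Table.** Recommended Dose Modifications for Nivolumab marks Grade 2 or 3 diarrhea or colitis, Grade 2 pneumonitis and the lower hepatitis band as withhold rows carrying footnote a. The footnote reads in full: "Resume treatment when adverse reaction returns to Grade 0 or 1". It names no exceptions and does not point back to the resume criteria.

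**The concern.** The resume criteria take these three event groups out of the general Grade 1 rule. The footnote applies the Grade 1 rule to exactly those rows. A site working from the table could re-dose while diarrhea/colitis, lung toxicity or a liver-test elevation is still above baseline. For liver tests and Grade 1 pneumonitis it could also do so before steroid treatment or the taper is complete.

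This is a participant-safety question in a trial planned for three sites. It also affects compliance review, because whether a Grade 1 restart counts as a deviation depends on which paragraph is read. It does not touch the sample size, the exact test of ORR or the error rates.

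**Working it through.** The plan has no figure to reproduce here. The check sets the two rules side by side and then sizes the gap where the documents allow.

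**1. Rows carrying footnote a.** Colitis, pneumonitis, hepatitis, hypophysitis, adrenal insufficiency, type 1 diabetes, nephritis, skin, encephalitis, other: 10 rows.

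**2. Rows where the list is stricter.**

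| Row | Footnote a | Criteria to Resume Dosing | Where they part |
|---|---|---|---|
| Grade 2–3 diarrhea/colitis | Grade 0–1 | Baseline; no steroid condition | Grade 1 now, none at baseline |
| Grade 2 pneumonitis | Grade 0–1 | Baseline, or persistent Grade 1 after a completed taper of at least 1 month | Grade 1 now, taper not complete |
| Hepatitis, lower band | Grade 0–1 | Baseline, with any steroid treatment complete | Grade 1 now and above baseline, or still on steroids |

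That is 3 of 10. Three limits apply:

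- Section 8.5 discontinues a Grade 3 non-skin drug-related event lasting more than 7 days, so the Grade 3 colitis case arises only for shorter episodes.
- The table itself discontinues Grade 3 or 4 pneumonitis.
- If baseline was already Grade 1, the required level is the same under both rules, but the liver-test steroid condition still differs.

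**3. Liver tests.** The hold bands start above 3 × ULN (AST/ALT) and above 1.5 × ULN (bilirubin). Taking those lower limits as the top of Grade 1, the footnote can clear restart at up to those values. The list's ceiling is the participant's own baseline. Ratio = footnote ceiling ÷ baseline.

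- Baseline at ULN: AST/ALT 3 ÷ 1 = 3.0; bilirubin 1.5 ÷ 1 = 1.5.
- Baseline at the Section 6.1 limits (3.0 × ULN and 1.5 × ULN): 3 ÷ 3.0 = 1.0; 1.5 ÷ 1.5 = 1.0.

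**4. Persistent Grade 1 pneumonitis.** Assume the taper starts with the hold and Grade 1 is shown at the first weekly check (day 7). The footnote then allows restart at day 7. The list allows it no earlier than the end of a one-month taper (28 to 31 days). The difference is 28 − 7 = 21 to 31 − 7 = 24 days, about 3 weeks. It shrinks if Grade 1 is reached later, if the event resolves to baseline, or if the taper began well before the next dose was due.

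**5. Rows where the list is looser.** There are at least three: hypophysitis and adrenal insufficiency controlled by physiologic hormone replacement, and the row for other Grade 3 reactions when fatigue improves to Grade 2. The list is also looser for any participant whose baseline is above Grade 1. This includes a Gilbert participant who enters with bilirubin above 1.5 × ULN (entry allows below 3.0 × ULN).

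**6. Precedence.** Nothing in Section 9 ranks the footnote against the list.

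**The case against.** The best reply is that the documents largely settle the matter. The delay criteria send sites to re-treatment criteria, and the next heading is Criteria to Resume Dosing. The bowel and lung bullet is mandatory in tone, while the table is headed as recommended. Footnote a can be read as shorthand for the general rule, and a site that follows the list for these three events will ordinarily satisfy the footnote too. Investigators may also hold a dose for anything that "in the judgment of the investigator, warrants delaying the dose of study medication", and Section 8.5 allows delays for long steroid tapers. On this view only a cross-reference is missing.

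Those cues are real and make the list the likelier intent. They do not decide it. The footnote is attached to event-specific rows, so the principle that specific text overrides general text does not dispose of it. Discretion to wait does not tell a site that Grade 1 is not enough.

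Three further points stand as limits:

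- Section 8.2 places the gastrointestinal, pulmonary and hepatic algorithms in the Investigator Brochure and Appendix 1. Their content was not available in the text reviewed, so the conclusion covers Section 9 only and does not predict what sites will do.
- The three-week figure belongs to one scenario. Under four-weekly dosing an event can start mid-cycle, and the gap could then shrink toward zero.
- A footnote confined to three event groups leaves the looser rows of step 5 unreconciled. That is deliberate, since reconciling them would loosen restart and is a clinical decision for the sponsor.

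**Conclusion.** The concern holds. As written, footnote a permits re-dosing that Criteria to Resume Dosing forbids in 3 of the 10 rows that carry it. For liver tests the permitted level runs from equal to the list's requirement up to 3.0 times (AST/ALT) or 1.5 times (bilirubin) that level, depending on a baseline between the eligibility limit and ULN. For persistent Grade 1 pneumonitis the list restarts about 3 weeks later than the footnote under the stated timing assumptions, and less otherwise. The documents give no event rate, so the number of participants affected cannot be estimated. This is a safety inconsistency that should be corrected; it is not a flaw in the efficacy design.

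**What to change.** Keep the sentence in footnote a and add an exception clause: *except that diarrhea/colitis, pulmonary toxicity and AST/ALT/TBILI elevations must meet the stricter conditions in Criteria to Resume Dosing.*

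The cost is one amended footnote and no new assessments. Some participants with these events will restart later than the table now allows, but no later than the list already requires. No row is loosened. For Gilbert participants with baseline bilirubin above 1.5 × ULN, the table's Grade 0 or 1 limit stays unless the sponsor decides otherwise.

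A single sentence giving the whole list precedence would also remove the conflict. If the sponsor prefers that, the protocol should state that participants with controlled endocrinopathies, Grade 2 fatigue or a baseline above Grade 1 could then restart earlier than the table now allows.

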10 ADVERSE EVENTS: LIST AND REPORTING REQUIREMENTS

10.1 Adverse Event

An adverse event (AE) is any untoward or unfavorable medical occurrence in a human participant, including abnormal sign, symptom or disease, temporally associated with the participant's participation in research, whether or not considered related to the participant's participation in the research. Abnormal results of diagnostic procedures are considered to be adverse events if the abnormality:

- results in study withdrawal
- is associated with a serious adverse event
- is associated with clinical signs or symptoms
- leads to additional treatment or to further diagnostic tests
- is considered by the investigator to be of clinical significance

Immune-mediated adverse events (IMAEs) are AEs consistent with an immune-mediated mechanism or immune-mediated component for which non-inflammatory etiologies (eg, infection or tumor progression) have been ruled out. IMAEs can include events with an alternate etiology which were exacerbated by the induction of autoimmunity. Information supporting the assessment will be collected on the participant's CRF.

We will be reporting AEs to regulatory authorities and ethics committees according to local applicable laws including FDA Code of Federal Regulations 21 CFR Parts 312 and 320.

All AEs must be documented as related or unrelated to study treatment and graded per CTCAE 4.03.

10.2 Serious Adverse Event

Adverse events are classified as serious or non-serious. A serious adverse event is any AE that is:

- fatal
- life-threatening
- requires inpatient hospitalization/prolongation of existing hospitalization. NOTE: The following hospitalizations are not considered SAEs:

- A visit to the emergency room or other hospital department < 24 hours, that does not result in admission (unless considered an important medical or life-threatening event) [1]
[SEP]
- Elective surgery, planned prior to signing consent
- Admissions as per protocol for a planned medical/surgical procedure
- Routine health assessment requiring admission for baseline/trending of health status (eg, routine colonoscopy)
- Medical/surgical admission other than to remedy ill health and planned prior to entry into the study. Appropriate documentation is required in these cases.
- Admission encountered for another life circumstance that carries no bearing on health status and requires no medical/surgical intervention (eg, lack of housing, economic inadequacy, caregiver respite, family circumstances, administrative reason)
- Admission for administration of anticancer therapy in the absence of any other SAEs (applies to oncology protocols)
- results in persistent or significant disability or incapacity
- a congenital anomaly or birth defect
- an important medical event

Important medical events are those that may not be immediately life threatening, but are clearly of major clinical significance. They may jeopardize the participant, and may require intervention to prevent one of the other serious outcomes noted above. For example, drug overdose or abuse, a seizure that did not result in inpatient hospitalization or intensive treatment of bronchospasm in an emergency department would typically be considered serious. Potential drug-induced liver injury (DILI) is also considered an important medical event. (See Section 10.10 for the definition of potential DILI.)

All adverse events that do not meet any of the criteria for serious events should be regarded as non-serious adverse events (AE).

Non-serious Adverse Event Collection and Reporting

Non-serious Adverse Events (AE) are to be provided to BMS in aggregate via interim or final study reports as specified in the agreement or, if a regulatory requirement [eg, IND US trial] as part of an annual reporting requirement.

Non-serious AE information should be collected from the start of a placebo lead-in period or other observational period intended to establish a baseline status for the subjects.

The collection of non-serious AE information should begin following consent. All non-serious adverse events (not only those deemed to be treatment-related) should be collected continuously during the treatment period and for a minimum of 100 days following the last dose of study treatment. Non-serious AEs should be followed to resolution or stabilization, or until it has been

determined that the study treatment or participation is not the cause, or reported as SAEs if they become serious. Follow-up is also required for non-serious AEs that cause interruption or discontinuation of study drug and for those present at the end of study treatment as appropriate.

10.3 Unanticipated Problem

An unanticipated problem is any incident, experience or outcome involving risks to participants or others in any human subjects research that meets all of the following criteria:

- Unexpected (in terms of nature, severity or frequency) given (a) the research procedures that are described in the IRB-approval protocol and informed consent document, and (b) the characteristics of the participant population being studied;
- Related or possibly related to participation in such research (e.g., there is a reasonable possibility that the incident, experience or outcome may have been caused by the procedures involved in such research); and
- Suggests that the research places participants or others at a greater risk of harm (including physical, psychological, economic or social harm) than was previously known or recognized.

10.4 Adverse Event Reporting Period

The study period during which adverse events must be reported starts on the day of consent and continues for at least 100 days following the last administration of study drug.

Baseline/Preexisting Condition

A baseline/preexisting condition is one that is present at the start of the study. A preexisting condition should be recorded as an adverse event if the frequency, intensity, or if the character of the condition worsens during the study period.

General Physical Examination Findings

At screening, any clinically significant abnormality should be recorded as a preexisting condition. At the end of the study, any new clinically significant findings/abnormalities that meet the definition of an adverse event must also be recorded and documented as an adverse event.

Post-study Adverse Event

All unresolved adverse events should be followed by the investigator until the events are resolved, the participant is lost to follow-up, or the adverse event is otherwise explained. At the last scheduled visit, the investigator should instruct each participant to report any subsequent event(s) that the participant, or the participant's personal physician, believes might reasonably be related to participation in this study.

Abnormal Laboratory Values

A clinical laboratory abnormality should be documented as an adverse event if any one of the following conditions is met:

- The laboratory abnormality is not otherwise refuted by a repeat test to confirm the abnormality
- The abnormality suggests a disease and/or organ toxicity

- The abnormality is of a degree that requires active management or meets criteria for a SAE (e.g., change of dose, discontinuation of the drug, more frequent follow-up assessments, further diagnostic investigation, etc.).

Hospitalization, Prolonged Hospitalization or Surgery

Any adverse event that results in hospitalization or prolonged hospitalization should be documented and reported as a serious adverse event unless specifically instructed otherwise in this protocol. Any condition responsible for surgery should be documented as an adverse event if the condition meets the criteria for an adverse event.

Neither the condition, hospitalization, prolonged hospitalization, nor surgery are reported as an adverse event in the following circumstances:

- Hospitalization or prolonged hospitalization for diagnostic or elective surgical procedures for a preexisting condition. Surgery should **not** be reported as an outcome of an adverse event if the purpose of the surgery was elective or diagnostic and the outcome was uneventful.
- Hospitalization or prolonged hospitalization required to allow efficacy measurement for the study.
- Hospitalization or prolonged hospitalization for therapy of the target disease of the study, unless it is a worsening or increase in frequency of hospital admissions as judged by the clinical investigator.

10.5 Recording of Adverse Events

At each contact with the participant, the investigator must seek information on adverse events by specific questioning and, as appropriate, by examination. Information on all adverse events should be recorded immediately in the source document, and also in the appropriate adverse event module of the case report form (CRF). All clearly related signs, symptoms, and abnormal diagnostic procedures results should be recorded in the source document, though should be grouped under one diagnosis.

All adverse events occurring during the study period must be recorded. The clinical course of each event should be followed until resolution, stabilization, or until it has been determined that the study treatment or participation is not the cause. Serious adverse events that are still ongoing at the end of the study period must be followed up to determine the final outcome. Any serious adverse event that occurs after the study period and is considered to be possibly related to the study treatment or study participation should be recorded and reported immediately.

10.6 Reporting of Serious Adverse Events

The Reference Safety Information in the Investigator Brochure serves as a reference to determine expectedness of SAEs for expedited reporting.

All Serious Adverse Events (SAEs) that occur following the subject's consent through 100 days after last dose of study drug must be reported to BMS Worldwide Safety, whether related or not

Columbia University Medical Center
Herbert Irving Comprehensive Cancer Center
Version Date: January 30, 2024

related to study drug. If applicable, SAEs must be collected that relate to any later protocol-specified procedure (eg, a follow-up skin biopsy).

Following the subject's consent, all SAEs, whether related or not related to study drug, are collected, including those thought to be associated with protocol-specified procedures. The investigator should report any SAE occurring after these aforementioned time periods, which is believed to be related to study drug or protocol-specified procedure.

- An SAE report should be completed for any event where doubt exists regarding its seriousness;
 - If the investigator believes that an SAE is not related to study drug, but is potentially related to the conditions of the study (such as withdrawal of previous therapy or a complication of a study procedure), the relationship should be specified in the narrative section of the SAE Report Form.
 - If the BMS safety address is not included in the protocol document (eg, multicenter studies where events are reported centrally), the procedure for safety reporting must be reviewed/approved by the BMS Protocol Manager. Procedures for such reporting must be reviewed and approved by BMS prior to study activation.
- An appropriate SAE form, such as the HICCC DSMC SAE Form, (e.g. ex-US = CIOMS form or USA = Medwatch form) should be used to report SAEs to BMS . The BMS protocol ID number must be included on whatever form is submitted by the Sponsor/Investigator.
 - The CIOMS form is available at: <http://www.cioms.ch/index.php/cioms-form-i>
 - The MedWatch form is available at:
<https://www.fda.gov/downloads/AboutFDA/ReportsManualsForms/Forms/UCM048334.pdf>
 - [name] and [contact]

In accordance with local regulations, BMS will notify investigators of all reported SAEs that are suspected (related to the investigational product) and unexpected (ie, not previously described in the IB). An event meeting these criteria is termed a Suspected, Unexpected Serious Adverse Reaction (SUSAR). Investigator notification of these events will be in the form of a SUSAR Report.

- Other important findings which may be reported by BMS as an Expedited Safety Report (ESR) include: increased frequency of a clinically significant expected SAE, an SAE considered associated with study procedures that could modify the conduct of the study, lack of efficacy that poses significant hazard to study subjects, clinically significant safety finding from a nonclinical (eg, animal) study, important safety recommendations from a study data monitoring committee, or sponsor decision to end or temporarily halt a clinical study for safety reasons.

Columbia University Medical Center
Herbert Irving Comprehensive Cancer Center
Version Date: January 30, 2024

- Upon receiving an ESR from BMS, the investigator must review and retain the ESR with the IB. Where required by local regulations or when there is a central IRB/IEC for the study, the sponsor will submit the ESR to the appropriate IRB/IEC. The investigator and IRB/IEC will determine if the informed consent requires revision. The investigator should also comply with the IRB/IEC procedures for reporting any other safety information.
- In addition to the Sponsor Investigator's responsibility to report events to their local HA, suspected serious adverse reactions (whether expected or unexpected) shall be reported by BMS to the relevant competent health authorities in all concerned countries according to local regulations (either as expedited and/or in aggregate reports).

SAEs, whether related or not related to study drug, and pregnancies must be reported to BMS within 24 hours (excluding holidays and weekends). SAEs must be recorded on either CIOMS, MedWatch form, or institutional equivalent & pregnancies must be reported on a Pregnancy Surveillance Form or can be submitted on the aforementioned SAE form to BMS.

- **SAE Email Address:** [contact] and [contact]
- **SAE [contact]
- If only limited information is initially available, follow-up reports are required. (Note: Follow-up SAE reports should include the same investigator term(s) initially reported.)
- If an ongoing SAE changes in its intensity or relationship to study drug or if new information becomes available, a follow-up SAE report should be sent within 24 hours (excluding holidays and weekends) to BMS (or designee) using the same procedure used for transmitting the initial SAE report.
- All SAEs should be followed to resolution or stabilization.

IRB Notification by Sponsor-Investigator

Reports of all events (including follow-up information) that meet the definition of an unanticipated problem posing risk to participants or others must be submitted to the IRB within one week (5 business days) following the occurrence of the unanticipated problem or the principal investigator's acquiring knowledge of the unanticipated problem in accordance with IRB policy. Additionally, the sponsor-investigator will submit a summary of all Unanticipated problems that occurred since the beginning of the study at the time of continuing review. Copies of each report and documentation of IRB notification and receipt will be kept in the Regulatory binder.

DSMC Reporting by the Sponsor Investigator

Serious adverse events not constituting unanticipated problems are to be reported to the HICCC DSMC. Reporting should occur within 24 hours of knowledge of the SAE occurring at our institution or affiliate sites.

Reporting to Drug Manufacturer by Sponsor-Investigator

The Sponsor-Investigator will report to investigational agent manufacturer any serious adverse

events that meet the reporting criteria to the Institutional Review Board as described in section 10.4 within 24 hours of becoming aware of it, so that these reports can be evaluated and included in the Investigator's Brochure and for IND safety submissions per regulations. Reporting will occur by sending the reporting form along with any additional documentation sent to the regulatory authorities.

At the time of IRB renewal or at the request of the manufacturer, the Sponsor- Investigator will submit a summary of all Serious Adverse Events that have occurred inclusive of all sites to manufacturer.

